**NCT03846635**

## **Introduction**

### **Specific Objective(s) with hypotheses**

The Handheld Infrared Thermometer to Evaluate Cellulitis (HI TEC) study is a pragmatic, prospective cohort study based at the McGill University Health Centre in Montreal, Canada. We hypothesize that skin surface temperature, as measured at the bedside with a handheld infrared thermometer, will have diagnostic utility in evaluating suspected cellulitis. We also hypothesize that a decrease in temperature differential between affected and non-affected skin will predict clinical response to treatment and could serve as a good surrogate marker for future clinical trials in cellulitis.

#### *Primary Objective*

1. To determine if the difference in skin surface temperature between a suspected area with cellulitis and non-affected areas is associated with an infectious disease physician's clinical diagnosis of cellulitis. An association would introduce a rapid, objective tool to help non-expert clinicians differentiate cellulitis from other non-infectious etiologies in the absence of subspecialty consultation. We hypothesize that the areas with cellulitis will have a higher surface temperature and be associated with a diagnosis of cellulitis as determined by the attending infectious diseases physician.

#### *Secondary Objective*

1. To determine if the change in surface temperature over the course of treatment for cellulitis is predictive of clinical response to therapy. A demonstrated association would allow clinicians to objectively assess treatment progress at the bedside as well as provide a good surrogate outcome in clinical trials. We hypothesize that the temperature

differential will decrease over the course of treatment and predict clinical improvement.

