This data will be collected and managed using either the REDCap electronic data capture tools hosted at the McGill University Health Centre or another secure database system requiring password protected individually identified user accounts to access it [11]. Data will initially be stored by MRN (without name) but after all follow up visits are complete will be coded to ensure patient confidentiality (one-way hash of the MRN). The infectious diseases clinicians will be blinded to the result of the surface temperature measurement.

We will then compare the temperature difference between the affected and non-affected limbs with the current gold standard: the clinical diagnosis of the attending infectious diseases physician. This will yield estimates of sensitivity and specificity of the diagnostic test using expert clinical judgement as the gold standard.

In patients with cellulitis who are admitted for intravenous antibiotic therapy, we will perform daily measurements as described above throughout their admission. We will continue to record clinical data and laboratory data as above throughout admission for these patients. We will ultimately use statistical methods to characterize the relationship between skin surface temperature, expert clinical diagnosis of cellulitis and response to therapy (length of stay, duration of therapy, need for escalation in therapy, etc).

The study will be conducted until enrolment is completed. The anticipated study dates are September 1st 2018 to January 1st 2019.

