### *Statistical Analysis:*

For our primary aim, classical 2 x 2 tables will be used to evaluate the sensitivity and specificity of skin surface temperature in predicting cellulitis, as diagnosed by the attending infectious diseases specialist. A temperature difference of 0.5°C between the area of suspected cellulitis and an average of non-affected areas will be considered significant in the first attempt.

With regards to our secondary aim, we will use multivariate analysis and logistic regression to determine relationships between change in temperature differential and clinical response. Response to therapy will be defined on the basis of clinical and laboratory data and will consider the following information:

- Days of fever (i.e the number of calendar days since enrolment in which a temperature of 38.0 or higher was recorded)
- Days of intravenous antimicrobial therapy for cellulitis
- Days of hospitalization for cellulitis (including days in the ER)
- Total number of days of antibiotics given for cellulitis
- Days to normalization of white blood cell count
- Days to normalization of C-Reactive Protein
- Patient reported outcomes:
  - Patient global impression of improvement scale
    - Select the option which best describes your cellulitis now, as compared to how it was when you arrived in the emergency department:
    - Very much better (1)
    - Much better (2)
    - A little better (3)
    - No change (4)
    - A little worse (5)
    - Much worse (6)
    - Very much worse (7)

*Study Funding and Compensation*

This study is not externally funded. The fees for purchasing the infrared thermometer will be borne by the investigators. Physicians and patients will not receive compensation for their participation in this pragmatic study.

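### In the Protocol's secondary analysis, the window for temperature change ends when the stay ends, so its association with hospital days (and largely IV days) is biased against the hypothesis

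*Protocol*

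**What the plan says.** **Predictor.** The Protocol's Secondary Objective is "To determine if the change in surface temperature over the course of treatment for cellulitis is predictive of clinical response to therapy". The same paragraph expects the differential to shrink during treatment.

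**Readings.** Under Study Protocol, the followed group is defined by "In patients with cellulitis who are admitted for intravenous antibiotic therapy", and for them "we will perform daily measurements as described above throughout their admission". The last available reading therefore falls at discharge, on a different day for each patient.

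**Outcomes.** Study Protocol describes "response to therapy (length of stay, duration of therapy, need for escalation in therapy, etc". The Statistical Analysis section lists, among others, "Days of intravenous antimicrobial therapy for cellulitis", "Days of hospitalization for cellulitis (including days in the ER" and "Total number of days of antibiotics given for cellulitis". It also lists fever days, days until white cell count and C-reactive protein normalise, and a seven-point patient global impression scale.

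**Model.** The Statistical Analysis section names multivariate analysis and logistic regression for change in the differential against response. It gives no reading time, landmark, per-day rate or adjustment for time observed.

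**SAP.** The section Analysis of Improvement of Cellulitis uses a different outcome: a lesion-size reduction of at least 20% at 48 to 72 hours, with a Youden cut-point on temperature difference. It does not mention the Protocol's duration outcomes, either to keep or to drop them. It does not say when the temperature difference is read, or whether it is a change from baseline.

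**The concern.** For hospital days, a whole-course change is complete only at discharge, when the outcome is already fixed. It cannot be used to predict that outcome.

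The predictor's window is also as long as the stay. A patient discharged on day 2 contributes two days of cooling and one discharged on day 10 contributes ten. Since the Protocol expects cooling under treatment, the size of the fall grows with time observed, even if speed of cooling says nothing about response. Longer stay is the worse outcome, so the built-in association runs opposite to the hypothesis.

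The secondary aim is meant to support bedside monitoring and a surrogate endpoint for trials. A result whose sign partly reflects length of observation could support neither.

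**Working it through.** **Figures in the plan.** The documents give no figure for this analysis. The sample-size statement (31 minimum, aim of 50) concerns the between-limb difference and is unaffected. The number of admitted patients, cooling rate, spread of stay and reading error are not given, so every numerical input below is an assumption.

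**Step 1: overlap by outcome.**

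| Outcome | Is the predictor window set by the outcome? |
|---|---|
| Hospital days | Yes, apart from any days before enrolment |
| IV days | Largely, since the followed patients are those admitted for IV therapy |
| Total antibiotic days | Loosely, since therapy may continue after discharge |
| Fever days, days to white cell or C-reactive protein normalisation | Not directly |
| Global impression scale | No, it is not a duration |

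**Step 2: mechanism without chance.** Let everyone start at differential B = 3.5 °C and cool at the same rate r per day. The fall by day t is B × (1 − e^(−rt)).

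| r per day | Fall by day 2 | Fall by day 10 |
|---|---|---|
| 0.15 | 3.5 × (1 − e^(−0.3)) = 0.91 °C | 3.5 × (1 − e^(−1.5)) = 2.72 °C |
| 0.3 | 3.5 × (1 − e^(−0.6)) = 1.58 °C | 3.5 × (1 − e^(−3)) = 3.33 °C |
| 0.5 | 3.5 × (1 − e^(−1)) = 2.21 °C | 3.5 × (1 − e^(−5)) = 3.48 °C |

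Cooling is identical, yet the ten-day patient always shows the larger fall.

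**Step 3: no link between cooling and stay.** Assumed inputs: baseline differential 3.5 °C (SD 1.2), reading error SD 0.5 °C, the three rates above (the same for everyone), and a skewed distribution of stay with a median of about 5 to 6 days.

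| r per day | Correlation of total fall with stay | Correlation of 48 h fall with stay | Significant positive result, total fall, n = 20 / 30 / 50 |
|---|---|---|---|
| 0.15 | +0.46 | 0.00 | 59% / 77% / 93% |
| 0.3 | +0.35 | 0.00 | 35% / 50% / 72% |
| 0.5 | +0.20 | 0.00 | 15% / 20% / 30% |

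The 48-hour fall is significant, in either direction, in about 5% of studies, as it should be.

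A separate simulation used n = 30, baseline 3 °C (SD 1), halving time 1.5 to 5 days, reading error 0.3 to 0.6 °C and median stay 5 days. It gave +0.22 to +0.46 for total fall, with p < 0.05 in 22% to 75% of studies.

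**Step 4: a true link exists.** The hypothesised sign is negative (larger fall, shorter stay).

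| Scenario | Total fall vs stay | 48 h fall vs stay |
|---|---|---|
| Faster coolers leave earlier | +0.07 to +0.30 | −0.41 to −0.09 |
| 10% barely cool and stay twice as long | −0.02 to +0.12 | −0.31 to −0.18 |
| 20–30% barely cool and stay twice as long | −0.23 to −0.03 | −0.46 to −0.26 |

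In each scenario the total fall lies above (less negative than) the 48-hour fall. In the first the sign is reversed, in the second the link is largely masked, and in the third it is only weakened.

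**Step 5: why the enrolment differential matters.** If patients with a larger enrolment differential stay longer, total fall correlates with stay at +0.64 to +0.74. In one such run (rate 0.5) the figure was +0.65. There the absolute 48-hour fall still correlated at +0.36, while the 48-hour fall as a percentage of baseline gave +0.01. Fixing the time alone is therefore not enough.

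**The case against.** The strongest reply is that the SAP, dated March 2020 and later than the Protocol's anticipated study dates, has its own improvement analysis in which stay and therapy days do not appear. Its outcome is already at a fixed early time. This stands: the bias does not arise there, and a reader should not infer that the SAP's lesion-response result is affected. But the SAP does not say that the Protocol outcomes are withdrawn, and it leaves the time of its own temperature reading open.

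Second, the Secondary Objective is not a variable definition. Daily readings would also support a slope, a fixed-day change or a repeated-measures model. That is fair: enrolment reading minus last reading is the natural reading of the text, not a stated formula. Still, no alternative is named, and the wording points to the whole course.

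Third, a reader might infer that a large fall will look like poor response, or that every listed outcome is affected. The documents support neither. The sign depends on inputs they do not give, and with a sizeable group of slow-cooling long-stayers the association keeps the hypothesised direction. The overlap is looser for antibiotic days and absent for the global impression scale.

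Fourth, the simulations are unadjusted correlations, whereas the plan names multivariate and logistic models on a response that weighs several items. The percentages therefore do not carry over to the planned models. The direction does, because no adjustment for time observed is specified.

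**Conclusion.** The point holds for the Protocol's secondary analysis as worded. Relating whole-course temperature change to hospital days, and largely to IV days, lets the outcome set the predictor's window. It moves the association upward, against the hypothesis. This can mask a true link and, under some assumptions, reverse it.

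The direction rests on one premise, which the Protocol itself states: the differential falls under treatment. The size (+0.20 to +0.46 with no link, against 0.00 at 48 hours) rests on assumed cooling, stay and error values and should not be cited as an estimate for this study. It would be worth correcting because the readings needed are already planned.

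**What to change.** 1. In the Protocol's Secondary Objective and Statistical Analysis sections, and in the SAP's Analysis of Improvement of Cellulitis for consistency, define the predictor as the change in differential from enrolment to one fixed early reading aligned with the SAP's 48-to-72-hour assessment.
2. Adjust for the enrolment differential.
3. For each Protocol duration outcome that is kept, count days from that reading onward.
4. State in the SAP which Protocol response outcomes are retained and which are dropped.

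**Cost.** No new measurements are needed, but some patients leave these analyses. Those discharged before the fixed reading have no value for the predictor, and those whose white cell count or C-reactive protein has already normalised have no remaining time to count. They may be the fastest responders, so their number and characteristics should be reported. The simulations have almost no discharges before day 2 and so do not show this loss. The SAP also limits follow-up to admitted patients who agreed to it, so the remaining sample may be small.

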## Background

Bacterial cellulitis is an infection of the skin and underlying soft tissue that is a leading cause of adult emergency room visits and an increasing cause of admission to hospital [1, 2]. As microbiological investigations are often uninformative [3], the diagnosis and management of cellulitis relies entirely on clinical judgment [4]. However, several non-infectious pathologies, including venous stasis, contact dermatitis, and lymphedema, can mimic the typical features of cellulitis [4, 5]. These mimics can lead to differences in diagnostic and therapeutic decisions among physicians [6]. Diagnostic uncertainty often results in antimicrobial use for non-infectious etiologies, which is estimated to cost up to \$515 million annually in the United States and contributes to the burden of nosocomial infections, such as *C. difficile* [7].

An objective metric to differentiate cellulitis from its non-infectious mimics would be of significant clinical utility. Elevated skin surface temperature at the site of erythema, which is a hallmark feature of bacterial infection, is an intuitive potential metric. Recent trials of skin surface temperature have shown promise [8, 9], but no study has yet combined a pragmatic bedside measurement tool with an infectious diseases specialist's diagnosis and treatment plan. This is the basis of our proposal.

## Innovation

If positive, our findings would have significant implications for both clinical practice and research. The practicality of the laser thermometer as a bedside diagnostic aid would reduce cellulitis misdiagnoses, improve patient outcomes, and optimize clinical resource use. Moreover, current Food and Drug Administration (FDA) guidelines specify that the primary efficacy endpoint of skin infection trials must be a precisely measured relative decrease in surface area of a lesion [10]. This is a cumbersome approach with minimal clinical utility and significant interobserver differences in measurement. If our results demonstrate that change in surface temperature predicts clinical response, this may become an alternative and more practical outcome measure for response to therapy which is robustly reproducible.

## Methods

A prospective cohort study of patients seeking medical attention for suspected cellulitis

will be established. The Royal Victoria Hospital, the Montreal General Hospital and the Lachine Hospital (Montreal, Canada) will be the only participating sites.

### *Study Population*

#### Inclusion Criteria:

- Age 18 years or older;
- English or French-speaking;
- Received an infectious diseases consultation to evaluate proven or suspected cellulitis of the upper or lower extremity, either unilaterally or bilaterally;
- Either no empiric antimicrobials received or, at most, antimicrobials begun within 24 hours of notification for enrolment.

#### Exclusion Criteria:

- Presumptive diagnosis of a soft tissue infection of the trunk, head or neck that does not also involve a limb;
- Patients with only one limb;
- Patients with significant neuropathies or autonomic syndromes that might affect thermoregulation, such as severe diabetic neuropathy or diabetic dysautonomia, neurologic neoplasms and known vitamin deficiencies;
- Soft tissue infections requiring definitive surgical source control, such as abscesses or necrotizing fasciitis.

### *Study Protocol*

Our research team will be notified of eligible patients by direct page or e-mail from the infectious diseases service when a new consultation for cellulitis is requested. Within 6 hours of this notification (and ideally as soon as possible), we will obtain informed consent and enrol the patient. After obtaining informed consent, we will use a non-contact infrared thermometer to measure surface temperature at the site of suspected infection as well other locations on the ipsilateral and contralateral limb. Specifically, in the upper extremities, the surface temperature of the hand (mid point of dorsum) forearm (halfway point at the dorsal surface), and upper arm (approximately 10 cm below acromion process, middle of lateral portion of arm) will be measured in both limbs regardless of site of suspected infection. In the lower extremities, the surface temperature of the foot (mid point on dorsum of foot), shin (middle of leg, approximately 10 cm below tibial tuberosity), and distal thighs (approx. 10cm above superior edge of knee,

middle of thigh) will be consistently recorded. All measurements will be made in triplicate for the first ten patients and if there is very high reproducibility of the measurements in those ten single measurements from then on. If there is moderate to high reproducibility of the measurements we will reduce to duplicate.

Relevant laboratory and clinical information will also be extracted from the chart. Clinical information will include age, sex, medical co-morbidities, medications and clinical measurements (such as vital signs). Biochemical data will include white blood cell count and C-Reactive Protein levels (when available). Microbiological data, including cultures of blood and purulent exudate, will also be considered when available. Treatment data on which antibiotics and duration of therapy will be obtained but only after all initial measurements have been taken to avoid any potential bias in measurement. Treatment data will include the name of the ID physician (all ID physicians will agree via the Divisional Chair) so that appropriate statistical testing can be done to account for differences in the “gold standard” between doctors.

This data will be collected and managed using either the REDCap electronic data capture tools hosted at the McGill University Health Centre or another secure database system requiring password protected individually identified user accounts to access it [11]. Data will initially be stored by MRN (without name) but after all follow up visits are complete will be coded to ensure patient confidentiality (one-way hash of the MRN). The infectious diseases clinicians will be blinded to the result of the surface temperature measurement.

We will then compare the temperature difference between the affected and non-affected limbs with the current gold standard: the clinical diagnosis of the attending infectious diseases physician. This will yield estimates of sensitivity and specificity of the diagnostic test using expert clinical judgement as the gold standard.

In patients with cellulitis who are admitted for intravenous antibiotic therapy, we will perform daily measurements as described above throughout their admission. We will continue to record clinical data and laboratory data as above throughout admission for these patients. We will ultimately use statistical methods to characterize the relationship between skin surface temperature, expert clinical diagnosis of cellulitis and response to therapy (length of stay, duration of therapy, need for escalation in therapy, etc).

The study will be conducted until enrolment is completed. The anticipated study dates are September 1st 2018 to January 1st 2019.

### *Sample Size*

In order to detect a 12% difference in skin surface temperature between limbs with a statistical power of 80%, assuming an alpha value of 5%, we anticipate that we will need to enrol 31 patients at a minimum. To be certain that we will establish reasonable sensitivity and specificity estimates and that our sample size will be sufficient, we will aim to enrol 50 patients with a diagnosis of cellulitis.

### *Statistical Analysis:*

For our primary aim, classical 2 x 2 tables will be used to evaluate the sensitivity and specificity of skin surface temperature in predicting cellulitis, as diagnosed by the attending infectious diseases specialist. A temperature difference of 0.5°C between the area of suspected cellulitis and an average of non-affected areas will be considered significant in the first attempt.

With regards to our secondary aim, we will use multivariate analysis and logistic regression to determine relationships between change in temperature differential and clinical response. Response to therapy will be defined on the basis of clinical and laboratory data and will consider the following information:

- Days of fever (i.e the number of calendar days since enrolment in which a temperature of 38.0 or higher was recorded)
- Days of intravenous antimicrobial therapy for cellulitis
- Days of hospitalization for cellulitis (including days in the ER)
- Total number of days of antibiotics given for cellulitis
- Days to normalization of white blood cell count
- Days to normalization of C-Reactive Protein
- Patient reported outcomes:
  - Patient global impression of improvement scale
    - Select the option which best describes your cellulitis now, as compared to how it was when you arrived in the emergency department:
    - Very much better (1)
    - Much better (2)
    - A little better (3)
    - No change (4)
    - A little worse (5)
    - Much worse (6)
    - Very much worse (7)

*Study Funding and Compensation*

This study is not externally funded. The fees for purchasing the infrared thermometer will be borne by the investigators. Physicians and patients will not receive compensation for their participation in this pragmatic study.

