Our goal was to detect a 12% difference in skin surface temperature between limbs with a statistical power of 80%. Assuming an alpha value of 5%, we estimated that we would need to enroll a minimum of 31 patients. To more confidently establish sensitivity and specificity estimates and to be more certain of an adequate sample size, we sought to enrol 50 patients.

With the “*cutpt*” command in STATA v. 16 (Statacorp LP, USA), we will use Youden’s method² to determine the temperature difference which best differentiated cellulitis from pseudocellulitis. We will then use bootstrapping (500 repetitions) to estimate 95% confidence intervals for the sensitivity, specificity and the area under the receiver operating curve (c-statistic). Then, using the point estimates for sensitivity and specificity we will construct a plot of pre-test vs. post-test probability as a function of test result. We will also calculate the temperature difference which gave the maximal specificity and include it for reference.

Analysis of Improvement of Cellulitis:

For those who were admitted to hospital and who agreed to be followed we will calculate the FDA criteria for early response (percent reduction in the lesion size at 48 to 72 hours compared to baseline) wherein clinical response in a patient generally is defined as a percent reduction in lesion size greater than or equal to 20 percent compared to baseline. With the “*cutpt*” command in STATA v. 16 (Statacorp LP, USA), we will use Youden’s method² to determine the temperature difference which best matches early response. We will then use bootstrapping (500 repetitions) to estimate 95% confidence intervals for the sensitivity, specificity and the area under the receiver operating curve (c-

statistic). We will also calculate the temperature differences which give the maximal sensitivity and specificity and include it for reference.

We will also explore the relationship between change in lesion size and temperature difference between limbs graphically and calculate an estimate of the correlation using the most appropriate regression method based on inspection.

REFERENCES

2. Youden WJ. Index for rating diagnostic tests. *Cancer.* 1950;3(1):32–35.

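### The SAP drops the Protocol's 0.5°C 2 x 2 analysis without explanation and reports sensitivity and specificity only at cut-offs chosen from the study data, uncorrected for optimism

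*Protocol*

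**What the plan says.** **Protocol, Statistical Analysis.** For the primary aim, "classical 2 x 2 tables will be used to evaluate the sensitivity and specificity of skin surface temperature in predicting cellulitis", with the infectious diseases specialist's diagnosis as reference. The threshold follows: "A temperature difference of 0.5°C between the area of suspected cellulitis and an average of non-affected areas will be considered significant". The sentence ends with a qualifier: "an average of non-affected areas will be considered significant in the first attempt". So 0.5°C is where the analysis starts, and later cut-offs are not ruled out.

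**Protocol, Primary Objective.** The question is one of association and names no cut-off: "To determine if the difference in skin surface temperature between a suspected area with cellulitis and non-affected areas is associated with" the specialist's diagnosis.

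**SAP, Analysis of Diagnosis of Cellulitis.** Youden's method is used "to determine the temperature difference which best differentiated cellulitis from pseudocellulitis". Then: "We will then use bootstrapping (500 repetitions) to estimate 95% confidence intervals for the sensitivity, specificity", and also for the AUC. The point estimates of sensitivity and specificity go into a plot of pre-test against post-test probability. A second cut-off, the one with maximal specificity, is given for reference. The SAP does not mention 0.5°C, gives no reason for leaving it out, and describes no validation or optimism correction.

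**Comparator.** The Protocol's Statistical Analysis section attaches 0.5°C to the suspected area against an average of unaffected areas. Its Study Protocol section speaks of limbs: "We will then compare the temperature difference between the affected and non-affected limbs with the current gold standard". The SAP's Diagnostic Procedure compares the affected area with the matching site on the opposite limb.

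**The concern.** The value 0.5°C is the only numeric diagnostic threshold in either document. Without it, every sensitivity and specificity in the SAP sits at a cut-off selected because it performed well in these patients. Such estimates tend to flatter the test, and more so when one diagnostic group is small. Here they also drive the figure a clinician would use at the bedside, so the bias passes into the post-test probabilities.

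A reader who compares the report with the Protocol would find the stated analysis missing, with no note of why.

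**Working it through.** **1. Side by side.**

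| | Protocol | SAP |
|---|---|---|
| Cut-off | 0.5°C to start with | Youden; maximal specificity |
| Source of cut-off | Stated in advance | Study data |
| Comparator | Average of unaffected areas (Statistical Analysis); limbs (Study Protocol) | Matching contralateral site |
| Cut-off-free measure | None stated | AUC |
| Optimism correction | Not needed at a fixed cut-off | None stated |

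Neither document gives an expected sensitivity, specificity or temperature distribution, so there is no accuracy figure to reproduce and the result at 0.5°C cannot be predicted. The minimum of 31 patients is stated without a standard deviation or a test. It cannot be reproduced and does not bear on this point.

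**2. Optimism of a cut-off chosen on the same data.** Let J = sensitivity + specificity - 1.

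- *From the SAP:* 50 patients; cut-off chosen to maximise J.
- *Assumed:* the split between cellulitis and pseudocellulitis, normal temperature differences with equal variance in both groups, and true AUC.
- *Model:* the separation between groups in SD units is d = √2 × z(AUC). For AUC 0.8, d = 1.414 × 0.842 = 1.19, and the best attainable true J is 2Φ(d/2) - 1 = 2Φ(0.595) - 1 = 0.448.
- *Method:* in each of 2,000 simulated trials, choose the cut-off c that maximises the observed J. Its true sensitivity is Φ(d - c) and its true specificity is Φ(c). Optimism is mean apparent J minus mean true J at the chosen c.

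| Cellulitis/not | AUC | Apparent J | True J | Optimism |
|---|---|---|---|---|
| 40/10 | 0.7 | 0.431 | 0.257 | 0.175 |
| 40/10 | 0.8 | 0.571 | 0.414 | 0.158 |
| 40/10 | 0.9 | 0.729 | 0.602 | 0.127 |
| 35/15 | 0.7 | 0.411 | 0.260 | 0.150 |
| 35/15 | 0.8 | 0.551 | 0.418 | 0.133 |
| 35/15 | 0.9 | 0.715 | 0.607 | 0.108 |
| 25/25 | 0.7 | 0.393 | 0.260 | 0.133 |
| 25/25 | 0.8 | 0.537 | 0.420 | 0.117 |
| 25/25 | 0.9 | 0.706 | 0.609 | 0.097 |

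(Differences were taken before rounding.) The range is about 0.10 to 0.18. With an uninformative test (AUC 0.5), true J is 0 but apparent J still averages 0.20, 0.18 and 0.16 for the three splits.

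The Protocol's Sample Size section aims for 50 patients *with* cellulitis, whereas the SAP says 50 patients. If there are 50 cases, optimism over the same AUC range is 0.13 to 0.18 with 10 non-cases, 0.09 to 0.13 with 20, and 0.07 to 0.09 with 50.

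**3. Effect on the post-test plot.** For 40/10 and AUC 0.8, mean apparent sensitivity/specificity is 0.77/0.80 and mean true 0.73/0.68.

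- Positive likelihood ratio = sensitivity / (1 - specificity): apparent 0.77/0.20 = 3.85; true 0.73/0.32 = 2.28.
- At an assumed pre-test probability of 50% (odds 1), post-test probability = LR/(1 + LR): apparent 3.85/4.85 = 79%; true 2.28/3.28 = 70%.

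**4. What a fixed cut-off would give.** It carries no selection bias, but precision stays limited. For an observed 80%, the Clopper-Pearson 95% interval is 66-90% with 50 patients in the group, 56-94% with 20 and 44-97% with 10 (group sizes assumed).

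**The case against.** The best case for the SAP has four parts.

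- **The primary question is answered.** A reader might infer that dropping 0.5°C leaves the Protocol's question open. It does not. The objective is association with the specialist's diagnosis, the SAP restates it, and the AUC addresses it without any cut-off. Only accuracy at 0.5°C goes unreported.
- **The threshold was provisional.** The Protocol's qualifier foresees other cut-offs, so using Youden's method is not in itself a departure. This stands. But leave to try further cut-offs is not leave to skip the stated one in silence.
- **No results-driven switch is shown.** A reader might infer one, because the SAP is dated 1 March 2020, after the anticipated end of study on 1 January 2019, and describes measurement in the past tense. The study dates are only anticipated, and neither document says when data were accessed or analysed. The SAP also words its analysis prospectively. The documents do not support the inference.
- **A between-limb 0.5°C table is not exactly the Protocol's rule.** This is correct, because that threshold is attached to an average of unaffected areas. It affects how the added table must be labelled. It also means that the comparator changed without comment.

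**Conclusion.** The concern holds in a limited form. The SAP omits the Protocol's 0.5°C 2 x 2 analysis without a reason, so no sensitivity or specificity will be reported at a cut-off fixed in advance. Those it does report are uncorrected for selection on the same data. The likely overstatement of sensitivity + specificity - 1 is about 0.10 to 0.18 for 50 patients. That figure rests on assumed splits of 40/10 to 25/25, true AUC of 0.7 to 0.9 and a normal equal-variance model. It is smaller if many more patients without cellulitis are enrolled.

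That the omission and the change of comparator are unexplained rests on the text alone and needs no assumption.

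**What to change.** In the SAP's Analysis of Diagnosis of Cellulitis:

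1. Add the 2 x 2 table at 0.5°C, with sensitivity and specificity and Wilson or Clopper-Pearson 95% intervals. Name the comparator: the SAP's contralateral site and, if the sites listed in the Protocol's Study Protocol section were recorded, also the Protocol's average of unaffected areas. Do not describe the between-limb version as the Protocol's pre-stated rule.
2. Label the Youden and maximal-specificity cut-offs exploratory, or correct them for optimism. To correct, choose the cut-off again within each bootstrap sample, take its accuracy there minus its accuracy in the full data, average that difference, and subtract it from the apparent estimate. Use the corrected values in the pre-test/post-test plot.
3. Record the change of analysis and of comparator as a dated deviation with the reason. Leave the Protocol's sentence, including its qualifier, unedited: removing the qualifier now would make a provisional threshold look firm.

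The cost is one more table (two if both comparators are available), a few lines of code and a short note, with no extra patients. The downside is that accuracy at 0.5°C, and the corrected estimates, may look less favourable than the fitted ones.
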